1.1.11 Correlative Studies

Many NSCLC are infiltrated with immunosuppressive immune cells and these tumor cells are known to secrete immunosuppressive cytokines (70, 71) and express immunoregulatory, checkpoint molecules that impair anti-tumor immunity. The two best characterized immune checkpoints are cytotoxic T-lymphocyte-associated antigen 4 (CTLA4) and programmed cell death protein 1 (PD1). (72) CTLA4, through interaction with its receptor, CD28, regulates the amplitude of the early stages of T cell activation and enhances Treg cell immunosuppressive activity. (73, 74) The primary role of PD1 is to limit T cell activity in the periphery. (75, 76) PD1 is highly expressed on Treg cells and is associated with increased Treg cell proliferation. PD1 mediates its effects on T cells upon interaction with its ligands PDL1 (B7-H1) and PDL2 (B7-DC). PDL1 is expressed by numerous cancer cells (77) and by myeloid cells within the tumor microenvironment (78). Numerous clinical trials have been performed using antibodies that inhibit immune checkpoints. Blockade of CTLA4 has shown promise in melanoma, but is associated with significant immune related toxicities. (72) Blockade of PD1/PDL1 axis has proven to be effective in clinical trials of NSCLC with an overall response rate of 20%; PD1/PDL1 blockade also resulted in fewer immune toxicity than blockade of CTLA4. (70, 79-82) While extremely encouraging and

promising, 80% of patients did not respond to checkpoint blockade, suggesting that additional optimization, patient selection and development of combination therapies are needed.

Several recent studies have indicated that treatment of human tumors with photodynamic therapy (PDT) can stimulate the host anti-tumor immune response (10, 11, 83) and potentially overcome tumor induced immunosuppression allowing for enhanced survival and opening a window for the use of immunotherapy. The purpose of these correlative studies is to assess whether treatment with biophysical modalities, such as PDT, affects the immune contexture of NSCLC patients. These patients tend to have an immunosuppressed immune contexture, which is associated with lower overall lymphocytes counts in the periphery, leading to higher neutrophil to lymphocyte ratios (NLR) that can be prognostic for treatment outcome (84), elevated levels of circulating regulatory T cells, myeloid derived suppressor cells (MDSC), PD1 expressing T cells, and PD-L1 expressing MDSCs. (71, 84, 85)

To assess the effect of I-PDT and/or PDT on the immune contexture of study patients we will use flow cytometry to examine changes in circulating levels of neutrophils, total lymphocytes (CD45⁺), MDSCs (CD45⁺, CD11b⁺, CD33⁺, HLADR¹⁰, CD14⁺ or CD15⁺ and PD-L1⁺), cytotoxic T lymphocytes (CD45⁺, CD3⁺, CD8⁺, Granzyme B⁺, Perforin⁺). Tumor tissue will be collected and used as antigenic material for analysis of tumor specific T cell function (ELISPOT) and examined by flow cytometry for changes in PD-L1⁺ MDSCs and cytotoxic T lymphocytes similarly as above in the circulation.

We will use de-identified CT scans from each patient to fabricate 3-D phantoms with 3-D printing technology of the airway and tumor. This model will be used to make a mold where we will fabricate a phantom with optical properties that mimic the calculated optical properties of the tumor. These phantoms will be used to test the accuracy of a new algorithm to compute optical properties, and if found accurate it will be considered in future clinical studies.

1.1.12 Optical and Oxygenation Measurements (optional)

It has been reported that oxygenated blood has lower absorption coefficient in comparison to deoxygenated blood (68). Our group and others have reported that increases in tumor hemoglobin oxygen saturation and vascular perfusion will increase tumor oxygenation and penetration of the Photrofrin®-exciting 630-nm illumination laser light (64-68). An increase in light penetration and tumor oxygenation are expected to be accompanied by improvement in tumor response to I-PDT.

Therefore, prior to and immediately after delivering the therapeutic 630-nm laser light, we will measure tumor tissue partial oxygen pressure (pO2), and we will perform in-vivo spectral interstitial transmittance measurements that will provide data that can be used to assess optical properties.

Tumor pO2 will be measured with a validated commercial system (OxyLiteTM Pro, Oxford Optronix North America, London, ON, Canada; Oxford Optronix Ltd, Abingdon, UK) (86, 87) with a sterile pO2 sensor (pO2 'Large Area' sensor, sterile, 5 m length; 1 mm2 sampling area, Oxford Optronix North America, London, ON, Canada; Oxford Optronix Ltd, Abingdon, UK). The sterile pO2 sensor will be placed into a sterile catheter (Bronchial Tube sterile, Best Medical International, Inc. Springfield, VA) to achieve rigidity. The end of the bronchial tube will be open (prior to treatment) to expose the end of the pO2 sensor that can be

inserted into the target tumor for 2-3 min to measure the tumor pO2. The sensor and the catheter will then be removed. The sensor and the catheter will be of single use.

The change in optical properties will be reflected in changes in light irradiance that we have shown to affect tumor response and we can measure with a light dosimetry system (40, 41). We will measure the transmission of the laser light (for 10-30 s) with an isotropic dosimetry fiber (IP, Medlight S.A. Ecublens, Switzerland) that will be connected to our customized light dosimetry to measure the transmitted laser light irradiance and fluence. This system is being used in several other Roswell Park IRB approved studies (I 67918, I 62118 and I 767720). The isotropic dosimetry fiber is a 3 m long and 1 mm in diameter optical fiber with 0.85 mm in diameter distal tip. This fiber will be attached to the outer surface of endoscope so that the detection end is at the end of the endoscope. The isotropic dosimetry fiber must be calibrated prior to each use. Consequently, the fiber will be submitted to high-level disinfection before and after use, following the clinical procedure used to disinfect the endoscope. Then the isotropic dosimetry fiber can then be reused in multiple patients.

In addition, we will use the standard endoscope camera to measure the light transmission. To that end, we will use a video capture device (USB 3.0 HD Video Capture Device, StarTech, Groveport, Ohio) to connect a video output port on the endoscope to a USB port on a password secured computer. The streaming software Stream Catcher Pro (StreamCatcherPro, StarTech, Groveport, Ohio) will be used in unison with the Startech system to allow for the recording of the endoscope video feed. Live feed from the endoscope camera is displayed on the software interface. This interface allows the user to name their recording, select the file format the video will be saved as, and then start and stop recording. All videos will be taken during treatment. Recordings save automatically with the given name and file type immediately upon stopping a recording. *This process does not interfere with the routine EBUS procedure*. It has been tested in [name] laboratory using a research clinical system (an Olympus endoscope) that is same as the system being used in the clinic. The recoded data will be saved and analyzed on a password secured computer in [name] laboratory.

2 RATIONALE

Chemotherapy remains the mainstay of treating inoperable malignant airway obstruction. Despite chemotherapy with one or more regimens, most patients will suffer recurrent disease and may present with airway obstruction. Some patients may develop respiratory symptoms (e.g., dyspnea, hemoptysis, post-obstructive pneumonia, respiratory failure) secondary to tracheal or bronchial obstruction. Palliation of their symptoms is usually accomplished by tumor irradiation or bronchoscopic intervention. For some patients, palliative radiation results in clinical improvement after partial or complete resolution of the airway obstruction. However, other patients may have no response to radiation, which results in disease progression and worsening of respiratory symptoms.

Bronchoscopic intervention leads to faster improvement but requires an advanced bronchoscopic procedure using laser, cryotherapy, tumor debulking, and ablation with or without airway stenting. Patients at this terminal stage tend to progress with recurrent airway obstruction, which can lead to repetitive palliative bronchoscopic procedures. There is an urgent need to offer these frail patients a treatment with minimal toxicity and morbidity, and that can reduce tumor-induced symptoms with a chance to improve their quality of life and perhaps their survival.

Multiple studies have shown that PDT can lead to tumor regression in lung cancer and other malignancies when the tumors are less than 1 cm in thickness. However, I-PDT is required to treat large tumors. In recent review papers, we highlighted future directions using I-PDT with treatment planning as a possible modality to treat patients with locally advanced cancer including intrinsic and extrinsic cancer that compromise the airway and are larger than 1 cm (22, 23). In these tumors, EBUS can be used to guide the insertions of the TBN into the tumor and the RD250 laser fiber can be inserted through that needle for intra-tumor illumination (Figure 1 and Figure 2). Recently, [name] (Co-Investigator) and his research team published the concept of using EBUS-TBN to guide I-PDT in the treatment of locally advanced lung cancer. (90) In addition, I-PDT and/or PDT can be used to treat endobronchial tumors. (22)

Our overall hypothesis is that EBUS-TBN guided I-PDT and/or I-PDT and preceded by p-XRT are safe and have the potential to treat the bulk of locally advanced lung cancer or other malignancies in the central airway, which may lead to tumor regression or slower progression and therefore a longer palliation period.

3 OBJECTIVES

3.1.1 Primary Phase I Objective (Cohort 0, data collection completed)

• For patients with locally advanced lung cancer (LALC) and malignancies causing airway obstructions: To evaluate the safety and potential efficacy of EBUS-TBN guided I-PDT and/or I-PDT and/or PDT, using porfimer sodium as a photosensitizer.

3.1.2 Primary Phase II Objectives (Cohort A and Cohort B)

- To assess the tumor response to treatment.
- To observe changes in well-being.

3.1.3 Secondary Objectives (Cohort A and Cohort B)

- To evaluate PFS.
- To compare the treatment planning in DOSIETM with the plan generated in COMSOLTM in Cohort A only.
- To measure changes in tumor pO2, optical properties, and irradiance and fluence in relationship to response.
 - •

3.1.4 Exploratory Objectives (Cohort A and Cohort B)

- Examine porfimer sodium retention in the target tumor tissue.
- Examine the relationship between immune biomarkers and response.

4 METHODOLOGY

4.1 Study Design

This is a multi-center, multi-arm, Phase I (Cohort 0; data collection complete) to monitor the safety and Phase II study (Cohort A and Cohort B described below) to monitor the efficacy of EBUS-

TBN guided I-PDT and/or I-PDT and/or PDT in patients with malignant airway obstructions that are refractory to curative chemoradiation or, who are not candidates for curative chemoradiation. Participants will be treated on an outpatient or inpatient basis, and the treating physician will make this decision on a case-by-case basis.

Cohort 0 is closed to accrual and fulfilled the Phase 1 safety monitoring requirements. Cohort 0 provided the safety monitoring component for Cohort A of this Phase II study. Cohort 0 consisted of patients with the diagnosis of lung cancer that received porfimer sodium with EBUS I-PDT and participated in all of the study procedures except the Quality of Life Questionnaires and Six Minute Walk Test.

Cohort A (n=18, Phase II) consists of patients with a diagnosis of lung cancer or other malignancies causing airway obstruction or inoperable malignancies not candidates for curative radiotherapy within the airway; and that receive EBUS I-PDT and all of the study procedures. Subjects treated in Cohort 0 are considered the Phase I part of Cohort A.

Cohort B (n=39) will consist of patients with the diagnosis of lung cancer or other malignancies causing airway obstruction, or inoperable malignancies not candidates for curative radiotherapy within the airway. Subjects in Cohort B will receive the EBUS-guided I-PDT 48 ± 4 h after standard of care palliative radiotherapy of 8 Gy x1.

NOTE: Given the nature of this advanced airway procedure, only the physician performing the procedure will be the consenter for the procedure as well as for the study.

All participants will undergo the standard of care interventional bronchoscopy procedure with an attempt to treat and resolve the airway obstruction using conventional methods such as mechanical debulking, tumor ablation, and/or airway stenting. Airway stenting will be performed before or after I-PDT and/or PDT, as necessary. Curvilinear EBUS with Color Doppler will be used to guide the intra-tumor fiber insertion.

In each procedure, the estimated percentage of obstruction will be documented before and after endobronchial debulking and ablation. Tumor debulking and ablation will be performed before EBUS-TBN with I-PDT and/or I-PDT and/or PDT. The airway obstruction severity is usually estimated based on the size of scope that can be passed through an obstructed airway and based on the size of the balloon used to dilate the obstructed airway.

Airway obstruction severity will be classified as(91): mild (<50%), moderate (50-70%), and severe (>70%).

The baseline obstruction to be used in the study will be the airway obstruction that was established before the I-PDT and/or PDT.

It is considered standard of care, and a commonly used approach, to use the Endobronchial Ultrasound (EBUS) in combination with therapeutic bronchoscopy. It is useful for diagnostics, as well as a tool to guide therapeutic bronchoscopy. EBUS helps demarcate the anatomy of the bronchial and peri-bronchial structures such as vascular and cardiac organs and thus, making the therapeutic procedure safer. (92)

For Cohort B participants only, standard of care palliative radiotherapy of 8 Gy x1 will be administered to the target tumor at day -2 just before systemic administration of 2 mg/kg porfimer sodium. This will be coordinated with the radiation oncologist.

Standard of care blood work and a repeat bronchoscopy and endobronchial ultrasound are completed within four weeks (± 2 week) after the airway intervention, depending on the severity of the disease and the clinical condition of the patient. A chest CT scan will be performed prior to the repeat bronchoscopy to evaluate the airway obstruction and the disease progression.

4.1.1 Primary Phase I Endpoint (Cohort 0, data collection completed)

• For patients with LALC or other malignancies in the central airway that may extend and involve the esophagus: The primary outcome is the safety of the I-PDT using EBUS-TBN and/or I-PDT and/or PDT, as measured by toxicity and adverse events (AEs). The AEs will be evaluated and graded according to the NCI Common Terminology Criteria for Adverse Events (CTCAE) v5.0.

4.1.2 Primary Phase II Endpoints (Cohort A and Cohort B)

- Objective tumor response (CR, PR, PD, and SD)
- The FACT-L Total Score related subscale
- 6-minute walk measures.

4.1.3 Secondary Endpoints (Cohort A and Cohort B)

- The number of bronchoscopies
- Evaluate progression free survival (PFS)
 - Compare the treatment planning in DOSIETM with the plan generated in COMSOLTM in Cohort A only.
- To measure changes in tumor pO2, optical properties, and irradiance and fluence in relationship to response.

All participants will sign an informed consent prior to study related tests and interventions. All participants will meet the inclusion and exclusion criteria summarized in Section 5.1 and Section 5.2.

4.1.4 Target Accrual and Study Duration

Eight patients in the Phase I (Cohort 0), and 18 patients will be enrolled in the Phase II Cohort A (8 already enrolled under Phase 1 portion of Cohort A from previous protocol version) and 39 in Cohort B (65 patients total). It is expected to have up to 32 patients enrolled from accompanying external sites and the remainder enrolled from Roswell Park. Accrual is expected to take up to 10 years.

Patients will be drawn from the interventional pulmonology practice and from referrals from medical oncologists. All patients will come off study at 24 weeks.

Enrolled patients who do not receive the I-PDT and/or PDT for any reason (such as patient withdrawal, safety or inability to deliver the I-PDT) will be replaced.

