12.1.4 Secondary Analysis

For both Cohort 0+A combined and Cohort B progression free survival (PFS) will be defined as the time from date of study treatment to the time of first observed disease progression (modified RECIST 1.1 criteria) at the treated tumor site or death due to any cause. PFS will be summarized using standard Kaplan-Meier methods, with median PFS and specified PFS rates estimated with 95% confidence intervals. The number of bronchoscopies will be summarized descriptively.

For Cohort A only we will measure agreement between DOSIETM and COMSOLTM treatment planning measures in n=18 subjects consisting of light intensity from each fiber (mW, and mW/cm), percent of tumor that receives ≥ 8.6 mW/cm² and ≥ 45 J/cm², the irradiance and fluence at the margins, the min, average and maximum irradiance and fluence in 100% of the tumor using the concordance correlation coefficient (76)(CCC) and Bland-Altman plots (77) for visual displays of agreement. We will calculate the one-sided 95% confidence interval for the CCC using a percentile bootstrap-t approach for each endpoint and we will calculate the 95% confidence interval display. Disagreement on a given measure will be inferred if the estimated CCC is below the lower bound of the one-sided 95% percentile confidence interval.

Tumor response as a function of STAT3 tumor conversion percentages (if possible) will be analyzed using logistic regression adjusted for age and sex.

The data from this trial will inform the design of a prospective Phase IIb randomized trial.

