12.1.6 Phase II Sample Size Justification (Cohort A and Cohort B)

Let π equal the proportion of CR+PR responses. The primary analysis, for Cohort A and Cohort B, will consist of a one-sided exact binomial test of H₀: π =0.05 versus H_a: π >0.05 at level α =0.05. Given n=18 subjects and setting power at 0.80 we will be able to detect an alternative response rate of π >0.29. The primary analysis for Cohort B will consist of a one-sided exact binomial test of H0: π =0.30 versus Ha: π >0.30 at level α =0.05. Given n=39 subjects (including n=6 from the Phase I) and setting power at 0.80 we will be able to detect an alternative response rate of $\pi > 0.50$. A secondary analysis of efficacy will utilize an ordinal regression of response (CR, PR, SD, PD) as a function of baseline tumor volume. All key secondary outcomes will be considered suitably continuous will be analyzed with an analysis-of-covariance (ANCOVA) approach regressing change from baseline to three months on the baseline value of the respective measure adjusted for baseline tumor volume, age, and sex. The null hypothesis of interest is H₀: $\beta_0=0,\beta_1=0$ versus H_a: $\beta_0 \neq 0, \beta_1 \neq 0$, where β_0 is the ANCOVA intercept and β_1 is the regression slope, respectively. All tests will be at level α =0.05. Since both the FACT-L based measures and the 6-minute walk measures are likely to be highly cross correlated no adjustments for multiple testing will be considered a priori. For Cohort A and Cohort B, each continuous endpoint and given n=18 subjects we will have 0.80 power to reject the joint null hypothesis if the slope and intercept account for 39% of the overall variation or larger in the given endpoint. For Cohort B, each continuous endpoint and given n=39 subjects we will have 0.80 power to reject the joint null hypothesis if the slope and intercept account for 20% of the overall variation or larger in the given endpoint.

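### The eight Cohort 0 patients are placed inside Cohort A's 18 by the text and on top of them by the total of 65, so Cohort A's accrual target and analysis set are contradictory

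*Combined protocol and SAP*

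**What the plan says.** Section 4.1.4 lists the groups side by side: "Eight patients in the Phase I (Cohort 0), and 18 patients will be enrolled in the Phase II Cohort A". A parenthesis attached to the 18 then reads "8 already enrolled under Phase 1 portion of Cohort A from previous protocol version", and the sentence closes with "39 in Cohort B (65 patients total". The opening paragraph of Section 12 repeats the parenthesis.

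Section 4.1 gives Cohort A as n=18, Phase II, and adds: "Subjects treated in Cohort 0 are considered the Phase I part of Cohort A". It also says that Cohort 0 "participated in all of the study procedures except the Quality of Life Questionnaires and Six Minute Walk Test".

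Elsewhere the two groups are kept apart. Section 12 assigns the secondary and exploratory endpoints to Cohort 0+A, apart from the software comparison, which is for Cohort A only. Section 12.1.4 opens: "For both Cohort 0+A combined and Cohort B progression free survival (PFS".

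The figure of 18 carries three analyses: the exact binomial test of response (12.1.6), the ANCOVA of FACT-L and walk measures (12.1.6, "each continuous endpoint and given n=18 subjects") and the DOSIE versus COMSOL agreement analysis (12.1.4). None of these places says whether Cohort 0 is in the 18.

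**The concern.** One sentence in 4.1.4 supports two incompatible counts. If the parenthesis is right, the total is wrong; if the total is right, the parenthesis is wrong. This is current operative text, and it decides when Cohort A accrual stops and who enters its analyses.

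The effect is most direct for FACT-L and the walk test. Sections 4.1.2 and 12 list both among the primary Phase II endpoints, and Cohort 0 contributes no data on either. A site or statistician who follows the parenthesis would stop Cohort A with 10 usable records for endpoints that were powered on 18.

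For tumour response, the question is whether the test includes Cohort 0 patients, whose data collection is complete and whose results Section 1.1.10 describes as already reported. Left open, that choice could be made with those outcomes in view.

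**Working it through.** **1. Counts.** Inputs from 4.1.4: 8, 18, 39 and a total of 65.
- Eight outside the 18: 8 + 18 + 39 = 65, which matches the stated total. New Cohort A patients: 18. Cohort 0+A: 8 + 18 = 26.
- Eight inside the 18: 18 + 39 = 57, which does not match. New Cohort A patients: 18 − 8 = 10.

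**2. FACT-L and walk ANCOVA.** Inputs from 12.1.6: n=18, α=0.05, power 0.80, 39% of variation explained, joint test of intercept and slope (2 df). The check uses a noncentral F with λ = n·R²/(1−R²), 2 numerator df and n−2 error df.
- The plan's figure: n=18, λ = 18 × 0.39/0.61 = 11.51, error df 16, power 0.793. This agrees with the stated 0.80 to rounding; exactly 0.80 needs R² of 0.394.
- At n=10: λ = 10 × 0.39/0.61 = 6.39, error df 8, power 0.449. Reaching 0.80 needs R² of about 0.59.
- If error df are also reduced for baseline tumour volume, age and sex (n−5), power is 0.774 at n=18 and 0.369 at n=10. The like-for-like pairs are therefore 0.79 against 0.45, or 0.77 against 0.37.

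**3. Response test.** Inputs from 12.1.3 and 12.1.6: one-sided exact binomial, null rate 0.05, α=0.05, alternative 0.29. The critical value r is the smallest for which P(X ≥ r | n, 0.05) ≤ 0.05; power is P(X ≥ r | n, 0.29).

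| n | tail at r−1 under 0.05 | r | actual α | power at 0.29 | rate with 80% power |
|---|---|---|---|---|---|
| 18 | 0.058 | 4 | 0.0109 | 0.812 | 0.285 |
| 10 | 0.086 | 3 | 0.0115 | 0.590 | 0.381 |

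The n=18 row reproduces the plan. The n=10 row applies only if the eight are inside the 18 and are then left out of the test.

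**4. Software comparison.** Section 12.1.4 fixes n=18 in Cohort A only. The documents do not say whether the Cohort 0 cases have DOSIE plans, so no revised n can be derived.

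**The case against.** The best defence is that the documents, taken together, point to 18 new patients. Only separate groups give 65. Section 4.1.4 says the 18 will be enrolled in Phase II, and the parenthesis refers to a Phase 1 portion, so a Phase I part of 8 and a Phase II part of 18 can coexist. The Cohort 0+A label would be redundant if A already contained 0. Sections 8.1.2 and 8.1.9 require FACT-L and the walk test in Cohorts A and B, and the footnotes to Table 1 exempt Cohort 0. Where a lead-in does count inside a cohort, 12.1.6 says so: Cohort B's 39 expressly include 6 from Phase I, with no such phrase for Cohort A.

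Most of this stands, and it makes 18 new patients the better-supported reading. It does not remove the conflict. The parenthesis is attached to the Phase II 18 and is repeated in the statistics section, and the Cohort B convention could as easily lead a reader to count Cohort A's Phase I patients inside its sample.

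A reader might infer more: that n is really 10 for the response test, the ANCOVA and the software comparison alike. The documents do not support that. Cohort 0 had every procedure except FACT-L and the walk test, so its responses could be pooled and n would remain 18. For the software comparison there is no information either way.

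A reader might also want to show how pooling known outcomes would distort the response test by supposing some number of Cohort 0 responders. No response count for Cohort 0 is given. The 3 of 10 in Section 1.1.10 is a survival figure, so any such calculation would rest on an invented input. Before any outcome is known, a pooled test of 18 has α 0.011 and power 0.81; the issue is that the eight patients' outcomes are no longer unknown.

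Finally, 12.1.3 and 12.1.6 call FACT-L and walk additional or key secondary outcomes, although 4.1.2 and Section 12 list them as primary. That bears on how much weight the power loss carries, not on whether it occurs.

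**Conclusion.** The point holds as a contradiction in the accrual target and analysis set for Cohort A: 10 or 18 new patients, and 57 or 65 in total. It is not established that any analysis has n=10.

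If the 18 are all new, every stated n and the total of 65 stand, and only the wording is wrong. If the eight are inside the 18:
- FACT-L and walk have at most 10 patients, and power at 39% of variation is about 0.45 instead of 0.79. This follows directly from Cohort 0 lacking those assessments, and assumes that all 10 have complete baseline and three-month data.
- The response test keeps n=18 only by pooling Cohort 0 patients whose results have been reported; excluding them gives power 0.59 at 29%.
- The effect on the software comparison cannot be determined.

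The repair is cheap and fixes when accrual stops and who enters the primary test, so it should be made.

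**What to change.** On the better-supported reading, state in 4.1.4 and Section 12 that the 18 Cohort A patients are new and exclude the eight Cohort 0 patients. Delete the parenthesis in both places and keep the total at 65. Say in 12.1.6 that n=18 for response, FACT-L and walk means these new patients. Use Cohort 0+A only for the secondary and exploratory endpoints that Section 12 assigns to it, which leaves out the software comparison.

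If the eight are meant to be inside the 18, correct the total to 57. Restate n=10 and its power for FACT-L, walk and any other measure that Cohort 0 lacks. State whether the response test pools Cohort 0 (n=18, with part of the outcome data already known) or excludes it (n=10, power 0.59 at 29%), and whether those eight patients have DOSIE plans.

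The first option costs a few sentences in two sections and no patients beyond the stated total. The second needs restated sample sizes and power, and acceptance of the lower power.
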